## Research Protocol/Protocol Addendum Template

---

providing basic descriptive statistics regarding the number of events in each arm at one-and three-month follow-ups.

**Sample Size:** Based on our prior work, we believe it is useful to choose suicidal ideation as our primary outcome. In our pilot study of VA BIC, which included nine Veterans undergoing the VA BIC intervention, we found a greater than five-point improvement in the Beck Scale for Suicidal Ideation (BSS) over the three months following inpatient mental health discharge. Five points is a clinically meaningful improvement on the BSS as it represents the mean difference in suicidal ideation between ambulatory and hospitalized psychiatric patients. Furthermore, in our pilot RCT of VA BIC on a VA inpatient unit we were also able to detect a statistically significant difference in BSS scores in a sample of 19 enrolled Veterans. Therefore, we will have sufficient power in this current pilot RCT to show a significant improvement in suicidal ideation if we enroll up to 25 patients.

### **Study Population and Recruitment**

We will coordinate with staff at the WRJ, Togus or Manchester VAMCs to gain lists of patients referred to or discharged from VA-CCN mental health treatment settings. Acquiring these lists is the most comprehensive and effective way to garner this group of patients. We may also coordinate with staff at the sites mentioned in staff meetings such as interdisciplinary rounds (IDR) to learn of eligible patients for our study. Once a patient has been identified, we will then go into the patient's medical record to confirm eligibility criteria are met and to obtain contact information including telephone numbers and street addresses. In addition, if feasible, the staff may also inform the patient about our study and ask the patient's permission for our study team to contact the patient to provide further information about the study. In this case, if permission is obtained, the staff member will document this information in the patient's medical record.

We will request a HIPAA waiver for screening purposes. For patients identified via medical records, study staff will mail them a brief letter explaining the study. We will then follow-up via phone approximately one week after mailing the letter. If patients are interested in the study, study staff will read a consent document to the patient, and the patient will decide whether they would like to participate. If they agree to participate, verbal consent will be obtained and recorded on the telephone consent document. For patients who are referred to us by treating mental health providers, we will call the patient to further discuss the study. The VA staff will document in the medical record that the patient has given permission for the study staff to contact the patient and to provide further information about the study. If the patients are interested in participating, study staff will complete the consent process via telephone or VVC.

In the case of the RCT, study staff involved in the recruitment and consent process will be blinded at the time of study allocation. During the course of the study, it will be impossible to blind the intervention staff or patients to treatment allocation; however, the outcome assessor will remain blind to study assignment throughout the trial. Patients will be instructed not to reveal their study assignment to the outcome assessor.

### ***Inclusion Criteria:***

- The patient was recently discharged from a VA-CCN mental health treatment setting
- The patient is at risk for self-harm based on expressed symptoms such as suicidal ideation of any severity, suicide attempt, or self-harm or the patient has been diagnosed with a mental health condition that is a known risk factor for suicidal behavior (e.g., depression, substance use disorder).
- Be a patient connected to the WRJ VAMC, the Togus VAMC, or the Manchester VAMC;

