### **Project Proposal, Phase 3, Aim 3**

To test our hypotheses as described above, we propose to conduct an assessor - blinded RCT comparing the BESST intervention plus standard care to standard care alone. We will enroll up to 25 patients who are 18 years or older and are being discharged from a VA-CCN mental health treatment setting. The primary aim is to determine whether the BESST intervention reduces suicidal ideation at one and three months after discharge. The secondary aim is to evaluate the impact of the BESST intervention on other related measures of suicide risk including hopelessness, social connectedness, fatal/non-fatal suicide attempts and treatment engagement.

**Randomization:** Prior to the start of study enrollment, the study team otherwise not involved in recruitment will independently prepare allocation cards using a permuted block schedule. The same study staff member will then put these prepared allocation cards into sealed, opaque, numbered envelopes. After obtaining consent and completing the baseline assessment (see description below), the study staff member will take the next numbered envelope from the box (described above) and open the envelope to determine the patient's assignment. In the event that the patient has been assigned to the intervention, the study staff will notify the intervention staff in order that the intervention staff can initiate the intervention. Otherwise, the patient will be informed that they have been assigned to usual care.

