**Baseline Characteristics:** We will collect socio-demographic data from the electronic medical record such as age, sex, marital status and service history (e.g., branch, era, combat exposure). We will also collect diagnostic information using either the MINI International Neuropsychiatric Interview (MINI), which has been validated against the Structured Clinical Interview for Diagnostic and Statistical Manual of Mental Disorders (DSM). The MINI is a short, structured diagnostic interview that, on average, takes about 15 minutes to administer. We will ask about any history of suicide attempts using the validated Columbia Suicide Severity Rating-Scale (C-SSRS). The C-SSRS includes a seven-item subscale that assesses for actual and interrupted suicide attempts.

**Primary Outcome (Suicidal Ideation):** The primary outcome will be assessed using the Beck Scale for Suicidal Ideation (BSS) (Specific Aim 1). Patients will be asked about their current suicidal ideation (i.e., past week) at baseline and at the one-month and three-month follow-up

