## Research Protocol/Protocol Addendum Template

---

assessments. The BSS is a self-reported questionnaire that assesses severity of suicidal ideation. The BSS measures attitudes, behaviors, and plans to die by suicide. Each item on the BSS is scored on a scale from 0 to 2 and the first 19 of the 21 items are used to calculate a total score ranging from 0 – 38. The BSS has high reliability and is a valid measure of suicidal ideation. The BSS may be a measure of risk of suicide. There is evidence that the BSS is measurement invariant across time.

**Secondary Outcome (Patient Engagement):** We will measure patient engagement in treatment at baseline and at follow-up assessments in two ways. First, we will examine healthcare utilization in the first three months after discharge. We will look at the amount of contact with mental health providers as well as the time to first mental health appointment after discharge. We will also evaluate evidence of disruptions of care such as no-show and cancelled appointments. We will abstract these measures from the electronic medical record. Since it is possible that some patients may receive portions of their care outside of the VA system, we will also ask patients to self-report on non-VA care. To gather data regarding the patient's sense of self-efficacy around managing their suicide risk after discharge, we will administer the validated Suicide-Related Coping Scale (SRCS). This SRCS includes 17 questions related to a patient's perception of their ability to cope with suicidal thoughts. Each item is assessed using a 5-point Likert scale and the measure has been developed based on two studies of suicide prevention strategies conducted within Veteran populations. The scale includes two subscales including an External Coping subscale and an Internal Coping Subscale. Both subscales have shown good acceptable internal consistency. The two factors are also sensitive to change over time. Higher scores on the scale suggest better coping. In addition to the SRCS, we will also measure the patient's general sense of self-efficacy using the General Self-Efficacy Scale (GSE). This is a valid scale of self-efficacy that is designed for the general population (12 years or older) and it has been tested in various countries.

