## Research Protocol/Protocol Addendum Template

behaviors. The scale asks the assessor to document the actual and potential lethality of these behaviors. The C-SSRS is widely used in the VA.

**Secondary Outcome (Substance use):** We will assess substance use at baseline and follow-up assessments using a timeline follow-back approach. This method is commonly used in research studies to assess substance use patterns.

**Study Design:** As shown in **Figure 3** below, patients allocated to the BESST intervention will meet with the intervention staff around the time of discharge. During this visit, the patients will receive a brief educational intervention. Depending on patient preference, this visit will occur over the phone (or VA Video Connect). Depending on patient preference, the regular contacts will occur in a private office on the WRJ VAMC campus, or the contacts will occur over the phone (or VA Video Connect).

**Figure 3.** Schedule of Assessments and Interventions.

BIC= VA Brief Intervention and Contact Program; D/C = discharge; dy = days; m = months; MH = Mental Health; T0, T1, T2 = assessment time points; wk = weeks

All patients (including patients randomized to the intervention) will have access to standard care. Furthermore, regardless of study assignment, all patients will undergo outcome assessment at baseline (0M), one month (1M), and three months (3M). These assessments will be conducted by the independent outcome assessor. We anticipate that, in most cases, the baseline assessment will occur around the time of discharge. However, because patients will be recruited remotely, we anticipate that the baseline assessments may in some cases happen a few weeks after discharge. Depending on patient preference, the independent outcome assessor will conduct the follow-up assessments in a private office on the WRJ VAMC campus, over the phone, or using VA Video Connect. The assessors will be blinded to study assignment and the patients will be instructed to not reveal their status to the assessor.

Because we are recruiting patients from a large geographic area (New Hampshire, Maine and Vermont), we anticipate that several enrolled patients will prefer phone (or VA Video Connect) over in-person follow-up. Fortunately, the assessment instruments that we selected for this study can be administered over the phone or in person.

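### Patients may enter on a diagnosis alone and start at or near BSS 0, and neither the allocation nor the stated primary model accounts for baseline BSS

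*Combined protocol and SAP*

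**What the plan says.** Eligibility has two routes joined by an alternative. One is symptoms, namely "suicidal ideation of any severity, suicide attempt, or self-harm". The other is a diagnosis, such as depression or substance use disorder: "or the patient has been diagnosed with a mental health condition that is a known risk factor for suicidal behavior". No criterion requires current ideation or a minimum BSS.

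Entry follows the stay: "The patient was recently discharged from a VA-CCN mental health treatment setting". The Study Design paragraph expects baseline around discharge in most cases, but adds that "we anticipate that the baseline assessments may in some cases happen a few weeks after discharge". The recall window is short: "Patients will be asked about their current suicidal ideation (i.e., past week) at baseline". The scale has a floor: "the first 19 of the 21 items are used to calculate a total score ranging from 0 – 38".

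The primary aim (Project Proposal, Phase 3, Aim 3) is a reduction in suicidal ideation at one and three months in up to 25 patients. Under Randomization, uninvolved staff "will independently prepare allocation cards using a permuted block schedule". No stratification factor, block size or ratio is given. The envelope is opened after consent and the baseline assessment.

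Under Statistical Analyses, Specific Aim 1, the mixed model has arm and continuous time as fixed effects and a random effect for the patient. No baseline BSS covariate and no arm-by-time term is named. The Sample Size paragraph relies on a gain of more than five points in nine treated inpatients and a significant result in a 19-patient inpatient trial. It calls five points clinically meaningful because "it represents the mean difference in suicidal ideation between ambulatory and hospitalized psychiatric patients".

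**The concern.** The primary outcome is a fall on a scale that stops at 0, yet the criteria do not require a patient to be above 0. Three features allow low baseline scores: entry on diagnosis alone, a baseline at or after discharge, and a one-week recall window. The figures behind the sample size come from inpatient samples, and that paragraph does not discuss where this wider post-discharge population will start.

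Two things are at stake:

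- **Dilution.** Patients at zero add little or nothing to a mean reduction, so the overall arm difference is smaller than the effect in patients with ideation.
- **Chance imbalance.** With about a dozen patients per arm, zero scorers can split unevenly. One arm then has more room to fall, and natural recovery or regression to the mean can imitate a treatment effect or hide one. If baseline is one of the modelled responses and the arm effect is pooled over visits, the imbalance passes straight into the estimate.

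**Working it through.** **The plan's own figure.** The claim of sufficient power with up to 25 patients cannot be reproduced, because no SD, target power or between-arm difference is stated. The checks below are sensitivity calculations.

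**Inputs.** From the documents: N = 25, a 5-point effect (a pre-post change in treated patients, used here only for illustration) and alpha 0.05. Assumed: two-sided testing, 1:1 allocation giving 13 and 12, no dropout, and K patients with baseline BSS 0.

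**Dilution.** If the 5 points arise only in patients above zero, the overall mean effect is 5 × (25 − K)/25.

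**Imbalance.** If allocation ignores baseline BSS, the number k of zero scorers in the arm of 13 is hypergeometric (25, K, 13). The probability wanted is that |k/13 − (K − k)/12| is at least 0.25.

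| K at zero | Share of 25 | Mean effect overall | P(gap of 25 points or more) |
|---|---|---|---|
| 3 | 12% | 4.4 | 0.10 |
| 5 | 20% | 4.0 | 0.16 |
| 8 | 32% | 3.4 | 0.20 |
| 10 | 40% | 3.0 | 0.23 |
| 12 | 48% | 2.6 | 0.24 |

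Two rows by hand:

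- K = 3: only all three in the arm of 12 reaches the threshold (3/12 = 25 points, exactly on it). The probability is C(12,3)/C(25,3) = 220/2300 = 0.096.
- K = 10: a 7 to 3 split gives 7/13 − 3/12 = 53.8% − 25.0% = 28.8 points and counts. A 6 to 4 split gives 46.2% − 33.3% = 12.8 points and does not.

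With K = 2 the largest possible gap is 2/12 = 17 points, so the probability is 0. A simulation with blocks of 4 and K = 10 gave 23%, matching the formula.

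**In BSS points.** If the other patients average 12 at baseline (assumption; range 8 to 16), a 25-point gap is a baseline difference of 0.25 × 12 = 3 points (range 2 to 4).

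**Power, illustration only.** Normal formula, 12 against 13, SD assumed and held fixed. With 0, 5 and 10 of 25 at zero, power is 88%, 71% and 47% at SD 4, and 55%, 38% and 24% at SD 6. Zero scorers would also change the SD and skew the scores, so these figures show direction rather than forecast power.

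**What a remedy buys.** In a simulation with 10 of 25 at zero and other inputs assumed, the SD of the estimated arm difference under unstratified allocation was:

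- 1.66 points with no adjustment
- 1.28 with a zero/above-zero term
- 0.86 with continuous baseline BSS
- 0.83 when stratified envelopes were added to continuous adjustment

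A second simulation (10 at zero, the others with mean 12 and SD 5, blocks of 4, a 5-point effect above zero only) compared unstratified with stratified envelopes, both with baseline adjustment. Power was 42.6% and 42.9%, and the SD of the estimate 1.26 and 1.24. The absolute values depend on the inputs. The common finding is that adjustment makes envelope stratification nearly redundant.

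**The case against.** The strongest reply is that the share at zero is unknown. Eligibility without ideation does not show that many such patients will enrol, and all come from recent mental health treatment, after which the Scientific Rationale places the highest suicide risk. This stands. A reader might infer that a large part of the sample will start at zero, but the documents support only that it can happen. That is why low values of K are shown.

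Second, a reader might infer that patients at zero cannot benefit. The Risks and Side Effects section expects worsening ideation in either arm, and preventing a rise would lower the treated arm's mean. This also stands. The dilution formula sets that benefit to nil, so it overstates the loss. It errs the other way for patients scoring 1 to 4, who cannot fall by five points yet are counted within the group averaging five.

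Third, a reader might infer that the five-point benchmark holds only for patients starting at 5 or more, or that the hospital-to-ambulatory fall is used up before baseline. Neither follows. Five points is a mean difference and the plan has no five-point responder endpoint. The inpatient gain is reported over the three months following discharge, and Preliminary Studies describes an ambulatory pilot trial that suggested improved ideation, though in patients at risk for suicide and without a BSS figure.

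Fourth, BSS is collected at 0, 1 and 3 months, and a repeated-measures model can use baseline as a response. That could partly offset an imbalance, but only with a term such as arm by time, and the plan states neither that term nor how baseline enters. This part of the objection does not remove the gap.

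**Conclusion.** The concern holds as a gap in the stated analysis. It is not an error in eligibility. Entry with no ideation is permitted, the scale has a floor at 0, and neither allocation nor model is said to use baseline BSS. On assumed shares of 3 to 12 of 25 at zero, a gap of 25 percentage points or more between arms has a probability of about 10% to 24%, and a 5-point effect confined to patients above zero averages 4.4 to 2.6 points overall. The true share could lie outside that range; at 2 or fewer such a gap cannot occur. The imbalance figures assume arms of 13 and 12, and the dilution figures assume no benefit at zero.

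Being a pilot does not dispose of the point, because the plan tests BSS at P < 0.05 and claims sufficient power. A reader might also infer that stratified randomization is required. The simulations do not support that: once continuous baseline BSS is in the model, stratification changes the precision very little.

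**What to change.** In Statistical Analyses, Specific Aim 1:

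1. Define the primary comparison as BSS at one and three months, adjusted for baseline BSS as a continuous covariate, or at least as zero versus above zero. Say that baseline then serves as a covariate and not also as a response.
2. Report the number and share at baseline BSS 0 by arm.
3. Pre-specify the arm effect among patients with baseline BSS above 0 as a supportive analysis. Adjustment handles imbalance and precision but not dilution, and this analysis shows the dilution. With 3 to 12 at zero it would rest on 22 to 13 patients, so it should be read as an estimate with its interval.

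Eligibility stays as it is. Two envelope series (baseline BSS 0 and above 0) are feasible because the baseline assessment precedes opening, provided the BSS is scored by then. They are optional and add little after step 1, at the price of an extra allocation step and a possible incomplete block in each series.

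The cost of steps 1 to 3 is one model degree of freedom and a few lines of SAP text, using a value already collected. The wording should be fixed before outcomes are examined by arm.

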## Research Protocol/Protocol Addendum Template

---

- Be a Veteran;
- Be 18 years or older;
- Be able to speak English;

### *Exclusion Criteria*

- Unable to provide informed consent;
- We do not plan to enroll any potentially vulnerable populations including prisoners, institutionalized patients, or involuntarily committed patients.
- Study physician deems the patient not clinically appropriate (e.g., patient is acutely, medically unstable). Note it is possible that a patient's clinical status could improve to the point where a patient could be approached about the study. This decision will be left to the clinical discretion of the study PI.

### **Informed Consent**

We are requesting an alteration of consent. Because we are recruiting patients from VA-CCNs that are located across several states (many of which are located at a sufficient distance from the WRJ VAMC), it is not feasible for us to recruit patients in person to obtain their written consent. Furthermore, we wish to mitigate potential delays in recruiting patients because the goal of the intervention is to address the needs of patients around the time of discharge. Therefore, we will only be able to recruit patients virtually and conduct the consenting process virtually. Because this is a minimal risk intervention, it is appropriate to obtain a telephone consent or consent via VA-Video Connect (VVC) from the patient, with plans to send them a copy of the consent form by U.S. mail. This approach also reduces the burden on the patient, especially if they do not have access to technology and could otherwise not participate in the study because they can't sign a form electronically.

### **Risks and Side Effects**

#### ***Potential Risks***

Because the study population is known to be at high risk for suicide and the study outcomes include suicidal ideation, suicide attempts, and suicide, we will treat these events as anticipated adverse events during the course of this study. We will also consider hospitalizations or emergency room for worsening psychiatric symptoms or suicidal behavior as anticipated adverse events.

We fully expect that patients may report worsening suicidal ideation or suicidal behaviors at the study assessments (i.e., baseline, one-month, or three-month,) regardless of whether they are assigned to the intervention or control condition. In addition, patients who receive the intervention may report worsening suicidal ideation or suicidal behavior during an intervention visit. We also expect that patients could be seen in the emergency room or be hospitalized because of any of the aforementioned events. Thus, we anticipate for the patients to continue with the study unless the patient requests to be removed from the study. In addition, as described in our **Safety Alert Protocol**, the study staff will immediately follow the safety alert protocol in response to any reports of worsening suicidal ideation or behaviors. If deemed clinical necessary, the patient will be connected immediately with required clinical treatment. All patients will continue to have access to standard-of-care of treatment during the study irrespective of their study assignment. Furthermore, all patients may continue any treatments that they were getting as part of their routine care prior to enrolling in this study.

